ABR	General Assessment and Registration form (ABR form), the application form that is required for submission to the accredited Ethics Committee; in Dutch: Algemeen Beoordelings- en Registratieformulier (ABR-formulier)
AE	Adverse Event
AR	Adverse Reaction
CA	Competent Authority
CCMO	Central Committee on Research Involving Human Subjects; in Dutch: Centrale Commissie Mensgebonden Onderzoek
CV	Curriculum Vitae
DSMB	Data Safety Monitoring Board
EU	European Union
EudraCT	European drug regulatory affairs Clinical Trials
GCP	Good Clinical Practice
GDPR	General Data Protection Regulation; in Dutch: Algemene Verordening Gegevensbescherming (AVG)
IB	Investigator's Brochure
IC	Informed Consent
IMP	Investigational Medicinal Product
IMPD	Investigational Medicinal Product Dossier
METC	Medical research ethics committee (MREC); in Dutch: medisch-ethische toetsingscommissie (METC)
(S)AE	(Serious) Adverse Event
SPC	Summary of Product Characteristics; in Dutch: officiële productinformatie IB1-tekst
Sponsor	The sponsor is the party that commissions the organisation or performance of the research, for example a pharmaceutical company, academic hospital, scientific organisation or investigator. A party that provides funding for a study but does not commission it is not regarded as the sponsor, but referred to as a subsidising party.
SUSAR	Suspected Unexpected Serious Adverse Reaction
UAVG	Dutch Act on Implementation of the General Data Protection Regulation; in Dutch: Uitvoeringswet AVG
WMO	Medical Research Involving Human Subjects Act; in Dutch: Wet Medisch-wetenschappelijk Onderzoek met Mensen

SUMMARY

Rationale: SGLT2 inhibitors such as ertugliflozin improve blood pressure and kidney outcomes in people living with diabetes through incompletely understood mechanisms, however, not all patients treated with SGLT2 inhibition have improved outcomes. Changes in kidney sodium handling is among the mechanisms by which SGLT2 inhibition may reduce blood pressure and drive beneficial kidney outcomes. This process is heavily dependent on daily sodium intake by patients receiving SGLT2 inhibitor treatment. In this study, the effect of daily sodium intake on SGLT2-inhibitor induced physiological effect is studied, including blood pressure regulation and kidney physiology.

Objective: Primary outcome: to investigate the modifying effects of WHO-recommended sodium intake (90 mmol per day) vs. high sodium intake (targeted at 250 mmol per day) on the effect of ertugliflozin 15 mg daily, versus placebo, on 24-hour blood pressure in overweight/obese adults with type 2 diabetes.

Study design: The study is a bi-center randomized, placebo-controlled, crossover intervention study. Total number of included participants is 34, which undergo 4 conditions in randomized order (randomization list generated by computer and supervised by pharmacy; blinded to investigator). While the treatment will be blinded for all participants, the sodium interventions are open-label.

Study population: 34 Adults living with type 2 diabetes. 18 - 85 years of age. Obese or overweight with BMI > 25 kg/m².

Intervention (if applicable): Cross-over design during 4 conditions. The 4 conditions are: 1) low-sodium diet; placebo; 2) low-sodium diet; ertugliflozin 15 once daily; 3) high-sodium diet; placebo; 4) high-sodium diet; ertugliflozin 15 mg once daily

Main study parameters/endpoints:

Primary endpoint is indicated above.

Secondary endpoint: To investigate the efficacy of ertugliflozin 15 mg daily, versus placebo, in overweight/obese adults with type 2 diabetes to reduce the hypertensive effects of a high-sodium diet (250 mmol per day) versus 24-h blood pressure measurement during participant's normal diet (170 mmol/per day) obtained at screening visit.

Exploratory endpoints: To investigate the modifying effects of WHO-recommended sodium intake (90 mmol per day) vs. high sodium intake (targeted at 250 mmol per day) on the effect of ertugliflozin 15 mg daily, versus placebo, on the following parameters in overweight/obese adults with type 2 diabetes on GFR by iohexol clearance, Hematocrit, Office blood pressure, Kidney oxygenation, Parameters of intra kidney hemodynamic function including ERPF by p-aminohippurate (PAH) clearance and renal vascular resistance, Body anthropometrics, Fasting plasma glucose, Albumin excretion rate (24 hour), 24-hr urinary glucose excretion, Urinary and plasma biomarkers.

Nature and extent of the burden and risks associated with participation, benefit and group relatedness:

There is no clear health benefit for the study participants, except that participation will provide insight into their sodium intake and knowledge how to reduce sodium intake to WHO-recommended amounts, which may benefit their long-term health. The short-term treatment with SGLT2 inhibitor ertugliflozin will not provide lasting benefits. On the other hand, the drug has little side effects, especially during short-term treatment, which will be closely monitored. The most commonly observed side effect (usually after more prolonged treatment) involves genital mycotic infections, which can easily be treated with antifungal topicals. Glucose levels and blood pressure are lowered during treatment. There are no health risks to short-term changes in sodium diet. Potential changes in blood pressure during the high-sodium diet are closely monitored. The study procedures are safe. There are no risks with undergoing MRI procedures and the use of iohexol and PAH to measure kidney hemodynamic function bears no risk, with >1500 tests carried out in our department. Burden of participants includes 5 visits (including screening); 4 visits where an MRI scan (duration 30 min) is performed and where 2 intravenous catheters are placed for tracer infusion during 2,5 hours; 13 24-hr urine collections and 5 24-hr blood pressure collections. A total of maximally 500 mL blood will be withdrawn over the course of a number of months. The study team will mitigate travel for the participants by collecting 24-hr blood pressure and 24-urine samples at home.

INTRODUCTION AND RATIONALE

Diabetic kidney disease (DKD) remains the leading cause of chronic kidney disease (CKD) and dialysis in the developed world, and a major cause of premature mortality. Sodium-glucose cotransporter 2 (SGLT2) inhibitors confer cardiovascular and renal protection in many, but not all people with type 2 diabetes (T2D) (1). Yet, the mechanisms of these salutary cardiorenal benefits remain unclear, and are incompletely explained by the modest improvements in blood pressure, glycemic control, body weight, and serum uric acid (2). A better understanding of the mechanism of cardio-renal protection in response to SGLT2 inhibition is therefore needed to determine which patients would see the greatest benefit from this drug class and also how to augment the beneficial effects with complimentary drugs and/or lifestyle changes such as changes in dietary sodium intake.

As stated, the mechanisms by which SGLT2 inhibitors such as ertugliflozin induce cardiorenal benefits are uncertain. With respect to cardiovascular outcomes, hematocrit was statistically the most important mediator of heart failure reduction in the EMPA REG OUTCOME study (3). This increment in hematocrit likely reflects a reduction in plasma volume, which has originally been proposed to be caused by natriuresis. However, several trials (4,5), including the recent DAPASALT study (6) have indicated that SGLT-2 induced natriuresis is mild in terms of absolute amount of sodium excretion, is very transient (e.g. likely only present within 12 hour of the first dose) and therefore has been doubted to a) be the cause for the increment in hematocrit and b) to mediate the cardiovascular benefits.

This may be different for kidney outcomes, as SGLT2-induced changes in the location of tubular sodium reabsorption (thus even with neutral effects on total body sodium excretion), can largely impact kidney physiology. As such, more distal tubular sodium reabsorption (distal of the macula densa) triggers activation of tubuloglomerular feedback reducing glomerular pressure (7,8). In addition to changes in glomerular pressure, SGLT-2 induced changes in kidney physiology may drive changes in kidney oxygen metabolism.

From a metabolic point of view, the kidneys are highly active and are second only to the heart with respect to oxygen (O_2) consumption per tissue mass. To sustain this activity, the kidneys rely on various substrates to generate adenosine triphosphate (ATP) including citrate, glutamine, glucose and free fatty acids (FFA) (9). The vast majority of ATP consumption in the kidney relates to sodium reabsorption, and glucosuria and single-nephron hyperfiltration results in increased filtered sodium and activity of Na^+/K^+ ATPase pump due to high tubular glucose and sodium reabsorption (10-12). In fact, animal models suggest that renal O_2 consumption is increased by 40% in all cortical segments and by 160% each in the S3 segment and medullary collecting duct (13-17). In animal models, SGLT2 inhibition attenuates single-nephron hyperfiltration (18) and have also been shown to improve renal oxygenation and ameliorate renal hypoxia (19). Thus the SGLT2-induced renal benefit may be driven by improvements in renal oxygen availability. In addition, changes in tubular sodium reabsorption increase renal EPO production, which, through enhanced erythropoiesis, is the most likely explanation for the increase in hematocrit.

Thus, whether SGLT2 inhibitors modulate natriuresis or not, changes in tubular sodium handling lead to reduction of hyperfiltration, renal oxygen consumption and enhanced EPO secretion that collectively are thought to drive beneficial cardiorenal outcomes, amongst several hypotheses; effects that may be dependent of the amount of dietary sodium intake as argued below.

SGLT2 inhibitors may alter other aspect of sodium homeostasis as well. People with T2D are known to be sensitive to excess sodium intake, which may results in extracellular volume (ECV) expansion and hypertension. This is different for healthy, lean people in whom

increased salt intake usually does not increase blood pressure. These individuals are termed sodium-resistant (20,21). High-sodium intake suppresses SGLT2 expression leading to natriuresis. An effect not observed in rodents with hyperglycemia (22). Thus, SGLT2 inhibition during high-sodium diet could restore this response.

While it was previously thought that sodium sensitivity is exclusively driven by differences in renal sodium excretion, in salt-resistant people, sodium may bind non-osmotically in tissues such as endothelial surface layers and the glycocalyx, preventing water retention and hypertension (23). Integrity of the endothelial surface layer is important for vascular dynamics, and glycocalyx injuries have been implicated in the progression of DKD and cardiovascular disease. Interestingly, the SGLT2 inhibitor empagliflozin was shown to decrease tissue sodium content as measured by MRI, which could theoretically reduce non-osmotic sodium storage (24). On the other hand, SGLT2-inhibitor induced improvements in endothelial function could drive opposite effects with improved non-osmotic sodium storage. Currently, the effects of SGLT2 inhibition on sodium sensitivity are unknown, while its effect on sodium sensitivity may become very relevant in people that consume excess sodium. Given the blood pressure lowering effects of SGLT2-inhibitors, that may be driven by improvements in endothelial function, one could hypothesize that SGLT2 reduce sodium sensitivity.

Dietary sodium intake may modulate the effects of SGLT2 on the kidney and beyond through several mechanisms, as excessive sodium intake has kidney hemodynamic effects. As such, high sodium intake has been shown to increase GFR and effective renal plasma flow (ERPF) in normoglycemic individuals, while blood pressure (MAP) increased to a smaller extent. Given that renal vascular resistance = $MAP/ERPF$, this parameter declined. Filtration fraction ($FF=GFR/ERPF$) increased in the overweight individuals, but not in lean persons (25). As people with T2D are almost all overweight or obese and are usually sensitive to the effects of high-sodium intake (26), the renal hemodynamic effects of SGLT2 inhibitors could be off-set by high sodium intake. This could be secondary to impairment of tubuloglomerular feedback as shown recently for ertugliflozin in rodent studies (27). In addition, given the potential beneficial effect of SGLT2 inhibitors on kidney oxygenation, large amounts of filtered sodium could off-set this mechanisms of action.

Observations have been done with this reasoning for RAAS blockers. They are renoprotective in people with diabetes, likely secondary to reducing glomerular pressure through efferent vasodilation and lowering of filtration fraction (26). In people with diabetic kidney disease, this renoprotective effect was markedly affected by sodium consumption, with better protection afforded with low-sodium intake (27,28). Also for vitamin D (29) and neprilysin (30), interactions with sodium diet have been observed, with less efficacy at higher sodium intake. Based on these observations, it is plausible that baseline sodium intake is an important mediator for the kidney hemodynamic response and kidney protective effect of ertugliflozin.

In conclusion, although SGLT2 inhibitors mitigate cardiorenal risk in people with T2D, the protective effects are incomplete in the majority of people, which may be driven due to co-medication and dietary factors such as sodium intake. Therefore, carefully designed mechanistic trials are needed to better understand the interplay between ertugliflozin and salt intake. Studies focusing on these interactions will allow researchers to assess the effects of SGLT2 inhibitors in combination with other drugs that affect sodium homeostasis and potentially modify salt intake to maximize treatment response. In addition, such studies may also help to explain differences observed between (outcome) trials, which have included different ethnicities that may also contribute to differences observed in renal outcomes due to differences in dietary habits.

[figure not shown]

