4.4 Sample size calculation

Based on previous studies in patients treated with SGLT2 inhibitors, we expect a change in systolic blood pressure of 6-8 mmHg during normal sodium intake (150 mmol/day) (6,7). Based on our hypothesis, this effect is increased on a low-sodium intake and reduced during high-sodium intake.

We expect a difference of 4 mmHg between the placebo-controlled effects of ertugliflozin on a low- versus high-sodium diet, with a conservative SD on this difference of 8 mmHg.

A total of 34 patients completing the study provide 80% power at a two-sided alpha of 0.05, to detect a 4 mmHg difference with the indicated SD of 8 mmHg. Drop-outs will be replaced.

Based on the RED study (7) and DAPASALT(6) study, the power needed to detect changes in GFR and hematocrit are of sufficient magnitude and therefore we expect sufficient power for these parameters as well. **We will include 34 individuals.**

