8.1.3 Other study parameters (if applicable)

To investigate the modifying effects of WHO-recommended sodium intake (90 mmol per day) vs. high sodium intake (targeted at 250 mmol per day) on the effect of ertugliflozin 15 mg daily, versus placebo, on the following parameters in overweight/obese adults with type 2 diabetes:

- GFR by iohexol clearance
- Hematocrit
- Office blood pressure
- Kidney oxygenation
- Parameters of intra kidney hemodynamic function including ERPF by p-aminohippurate (PAH) clearance and renal vascular resistance
- Body anthropometrics
- Fasting plasma glucose
- Albumin excretion rate (24 hour)
- 24-hr urinary glucose excretion
- Urinary and plasma biomarkers

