- 5) **Body-impedance analysis.** To measure body fat content we will use the tetrapolar Soft Tissue Analyzer® (STA, Akern, Florence, Italy), which can perform Bio-Impedance Analysis (BIA). This technique measures the resistance in the body tissues when a 50 kHz AC electrical current is given between four electrodes. Resistance can be measured by placing two electrodes on the dorsal hand and two on the foot at the unilateral side of the body (Lukaski & Bolonchuk, 1988). Extracellular water (ECW) as a percentage of total body water (TBW) and body cell mass (BCM) will be calculated independent of weight and height.
- 6) **ECG:** A 12-leads ECG will be made in the fasting resting state during screening in order to assess cardiac conduction parameters. Heart rate on the ECG will be defined as the mean rate of 10 R-R intervals. PQ-time, QRS-time and QT-time will be calculated, QT-time will be corrected for heart rate by using the Bazett formula (C. Bazett, 2006). The cardiac vector and ECG morphology will be assessed.
- 7) **Blood pressure and heart rate (office):** Blood pressure and heart rate will be measured using an automatic oscillometric device (Dinamap®, GE Healthcare) After an acclimatization period of >5 minutes, blood pressure will be measured three times at the non-dominant arm, with the subject in a semi-recumbent position, using an appropriate cuff-size. The mean of the last 2 measurements will be used as final value (Mengden et al., 2010; Pickering et al., 2005).
- 8) **GFR** is measured by steady-state plasma iothexol concentrations measured at T=120 and T=150 as done in our previous approved protocols.

9) **ERPF** is measured by steady-state plasma PAH concentrations measured at T=120 and T=150 as done in our previous approved protocols.

10) **Filtration fraction** (GFR/ERPF) and renal vascular resistance (ERPF/mean arterial pressure) are calculated.

12) **24-hour blood pressure** is derived from Mobil-O-graph devices (24 ambulatory blood pressure monitors, The Netherlands), which will be available at both sites.

Daytime systolic blood pressure (SBP), daytime diastolic blood pressure (DBP), nighttime SBP, daytime DBP and nocturnal dipping pattern (in mmHg) are recorded.

12) sodium sensitivity is calculated as following: changes in blood pressure due to the high-sodium diet versus diet at screening (estimated based on experience/previous trials at ~165-170 mmol/day) and the effect on this parameter by ertugliflozin versus placebo.

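### Renal vascular resistance in 8.3 item 10 is the inverse of the Introduction's formula, and neither form corrects plasma flow for hematocrit, which the drug is expected to raise

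*Combined protocol and SAP*

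**What the plan says.** Section 8.1.3 lists among the exploratory parameters "Parameters of intra kidney hemodynamic function including ERPF by p-aminohippurate (PAH) clearance and renal vascular resistance". Two formulas for the resistance appear.

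- **Introduction and Rationale**, in an account of an earlier sodium study in normoglycemic people: "Given that renal vascular resistance = $MAP/ERPF$, this parameter declined".
- **Section 8.3, item 10**, the operational definition for this trial: "and renal vascular resistance (ERPF/mean arterial pressure) are calculated".

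Under item 9 of section 8.3, ERPF "is measured by steady-state plasma PAH concentrations measured at T=120 and T=150", so it is a flow of plasma, not of whole blood. No section converts it to renal blood flow.

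On hematocrit, the Introduction says that changes in tubular sodium reabsorption "increase renal EPO production, which, through enhanced erythropoiesis, is the most likely explanation for the increase in hematocrit". Section 4.4 counts on being able to detect a change: "the power needed to detect changes in GFR and hematocrit are of sufficient magnitude". The flow chart in section 8.3 puts hematocrit and ERPF on the same Day 10 visit of each block. Item 13 of that section adds whole-blood flow in the renal artery by phase-contrast MRI, but does not link it to the resistance.

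Sections 10.1 and 10.3 apply the same analysis to every exploratory variable: main effects of diet and drug, and their interaction.

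**The concern.** Resistance is driving pressure divided by the flow of whole blood. A ratio built on plasma flow follows resistance only while the plasma fraction of blood, 1 - Hct, stays the same across the conditions compared. Here the drug is expected to change that fraction. Randomisation and the crossover do not remove the problem, because the hematocrit shift is itself an effect of treatment.

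The inverted formula makes it worse. ERPF/MAP rises when resistance falls, so a value reported as resistance under item 10 would point the wrong way, with the hematocrit component on top. In a mechanistic study, the reading of a drug effect on renal vascular tone depends on both matters being settled before the data are seen.

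**Working it through.** **Plan's own figure.** The documents give no numerical value, expected change or power calculation for renal vascular resistance. The sample size of 34 in section 4.4 rests on 24-hour blood pressure and does not depend on this point.

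**Inputs.** The formulas, the use of plasma PAH and the expected direction of the hematocrit change come from the documents. The starting hematocrit (42%), the size of the rise (1 to 3 points) and the 5% pressure fall in step 3 are assumptions; the documents state none of them.

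**Step 1: algebra.** Write RBF for renal blood flow.

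- ERPF = RBF x (1 - Hct)
- MAP/ERPF = (MAP/RBF) / (1 - Hct)
- ERPF/MAP = (RBF/MAP) x (1 - Hct)

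With MAP and RBF fixed, a change from Hct0 to Hct1 multiplies MAP/ERPF by (1 - Hct0)/(1 - Hct1) and ERPF/MAP by the reciprocal. MAP/RBF does not change.

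**Step 2: size at fixed pressure and blood flow, from 42%.**

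| Hematocrit rise | MAP/ERPF (Introduction) | ERPF/MAP (8.3 item 10) | MAP/RBF |
|---|---|---|---|
| 1 point | 0.58/0.57: +1.8% | 0.57/0.58: -1.7% | 0 |
| 2 points | 0.58/0.56: +3.6% | 0.56/0.58: -3.4% | 0 |
| 3 points | 0.58/0.55: +5.5% | 0.55/0.58: -5.2% | 0 |

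For starting values of 38% to 45% and rises of 0.5 to 3 points, the ranges are +0.8% to +5.8% for MAP/ERPF and -0.8% to -5.5% for ERPF/MAP.

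**Step 3: pressure falls as well.** Take a 5% fall in MAP, unchanged RBF, and hematocrit rising from 42% to 44%.

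- MAP/RBF: 0.95, a fall of 5.0%.
- MAP/ERPF: 0.95 x 0.58/0.56 = 0.984, a fall of 1.6%. Of the 5.0-point fall, 3.4 points are hidden, about two thirds.
- ERPF/MAP: 1/0.984 = 1.016, a rise of 1.6%. Under the label that item 10 gives it, this would read as higher resistance when resistance has fallen.

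**Step 4: the diet-by-drug contrast.** If the drug changes 1 - Hct by the same proportion on both diets, the factor cancels in the ratio of the two drug effects. If hematocrit rises 1 point on one diet and 2 points on the other, both from 42%, the contrast in MAP/ERPF shifts by (0.58/0.56)/(0.58/0.57) = 0.57/0.56, or +1.8%.

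**Step 5: the corrected ratio.** MAP x (1 - Hct)/ERPF equals MAP/RBF. It shows 0% change in step 2 and the full 5.0% fall in step 3.

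**The case against.** The case against making much of this has several parts.

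- **The Introduction's formula is background.** It explains an earlier study and does not define this trial's endpoint. That is so; the definition at issue is item 10 of section 8.3, which also omits hematocrit.
- **A reader might infer that a hematocrit rise will be reported as a rise in resistance, that is, as vasoconstriction.** The documents do not support that. Under item 10 the same rise lowers the reported number. Even for MAP/ERPF, a net rise needs pressure and flow to stay roughly constant, whereas section 4.4 expects systolic pressure to change by 6-8 mmHg on this drug class. Only the bias relative to MAP/RBF is established.
- **A reader might infer that the interaction, the stated objective for this parameter, is biased too.** That needs a hematocrit response that differs by diet. The Introduction says only that excess sodium may expand extracellular volume; it reports no effect on hematocrit.
- **The size is assumed.** The hematocrit finding from the earlier outcome study ("hematocrit was statistically the most important mediator of heart failure reduction in the EMPA REG OUTCOME study") concerns mediation with another drug. It gives no value for 10 days of ertugliflozin.
- **The plasma-based index might seem impossible to compare with MRI flow.** It can be compared once ERPF is divided by 1 - Hct, and all the inputs are collected.
- **ERPF and hematocrit are themselves listed parameters**, so a careful reader of the results could see a hematocrit shift. This lessens the harm but does not correct the derived ratio.

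These points limit the claim. They leave the omission and the contradiction between the two formulas in place.

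**Conclusion.** The concern holds in limited form. The two formulas contradict each other, and both leave out a quantity that the protocol expects the drug to change. The drug main effect on the resistance measure therefore contains a hematocrit component. If the assumed rise is 1 to 3 points from 42%, that component is +1.8% to +5.5% in MAP/ERPF and -1.7% to -5.2% in ERPF/MAP. The algebra is certain. The size rests on assumed hematocrit values, and the sign of the net reported change cannot be known in advance. The interaction is affected only if the hematocrit response differs by diet. The primary and secondary endpoints and the sample size are untouched. This is a minor improvement to one exploratory parameter.

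**What to change.** In section 8.3 item 10, reconcile the orientation with the Introduction and state the derivation:

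- Renal blood flow = ERPF/(1 - Hct).
- Renal vascular resistance = MAP/renal blood flow = MAP x (1 - Hct)/ERPF, with Hct taken from the Day 10 sample of the same visit.

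Use this definition when analysing the parameter in section 8.1.3. If MAP/ERPF is kept for comparison with earlier work, label it a plasma-flow index and report it beside the corrected value. Renal artery flow from the phase-contrast MRI can serve as a cross-check.

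**Cost.** A short change to the derivation and no new data. The corrected value carries a little hematocrit assay error, is tied arithmetically to hematocrit (itself an exploratory parameter), and is less directly comparable with earlier MAP/ERPF reports. Settling it beforehand avoids a choice between definitions after the results are known.
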